4.0 Test Schedule

Cycle = 28 days

Tests and procedures	Active Monitoring Phase						
	≤14 days prior to registration	Cycle 1 Day 1 (± 2 days) prior to treatment	Cycle 1 Days 8, 15, 22 prior to treatment	Cycle 2 and beyond Day 1 (± 2 days) prior to treatment	Q 8 weeks from Cycle 1 Day 1 (± 5 days)	Every 3 Cycles starting at end of Cycle 3 (± 5 days)	End of treatment
History and exam, wt, ECOG	X			X			X
Height, Child Pugh score	X						
Vitals ³	X	X	X	X			X
Hematology group WBC, ANC, Hgb, PLT	X	X	X	X			X
Chemistry group Sodium, potassium, chloride, bicarbonate, total protein, albumin, calcium, glucose, BUN, total bilirubin, creatinine, alkaline phosphatase, SGOT (AST), SGPT (ALT)	X	X		X			X
Amylase ^R	X	X	X	X			
Lipase ^R	X	X	X	X			
CA19-9		X		X ⁵			
EKG ^R	X					X	
Echocardiogram	X			X ¹⁰			
Tumor measurement and Imaging (CT or MRI as clinically)	X ¹				X ²		

indicated)							
Pregnancy test	X ⁴						
Patient questionnaire booklet	X ⁹			X ⁹			
Adverse event assessment	X		X	X			
Research Archival Tissue (optional)	X ⁸						
Research Tissue Biopsy (optional)				X ^{7,R}			X ⁶
Research blood samples (Optional)	X			X			X

1. Imaging studies such as CT scans, and MRIs can be performed ≤ 28 days prior to registration. Use same imaging throughout the study. Assessment by physical exam should be done ≤ 14 days prior to registration.
 2. Tumor assessment must be performed at least every 8 weeks. Tumor assessment should be performed at any time during the treatment cycle that disease progression is clinically suspected so that patient can go off treatment and receive other therapy.
 3. Includes weight, blood pressure, pulse and temperature
 4. Women of childbearing potential only. Must be done ≤ 7 days prior to registration.
 5. Only to be collected if $> \text{ULN}$ on Cycle 1 Day 1
 6. If patient has experienced disease progression and at such time a standard of care biopsy is ordered by the treating physician, waste specimen will be collected, fresh frozen and stored for future correlative studies. Perform only if archival specimen was available.
 7. Perform only if archival specimen was available.
 8. Archival FFPE and/or fresh frozen tissue collected in setting of standard of care procedures.
 9. Patient questionnaire booklet must be used; copies are not acceptable for this submission. Booklet should be completed by patient prior to review of treatment response and discussions of patient's general health since last treatment evaluation.

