 - 10 Echocardiograms to be completed at baseline and then every 2 cycles for the duration of study treatment.
- R Research funded (see Section 19.0).

5.0 Stratification Factors: None.

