	Alanine aminotransferase increased (ALT) OR Aspartate aminotransferase increased (AST) ≥ Grade 3 AND Blood bilirubin increased ≥ 2 x ULN AND Alkaline phosphatase > 2 x ULN	Ponatinib	Discontinue ponatinib
Gastrointestinal Disorders	Pancreatitis ≥ Grade 2	Ponatinib	Omit ponatinib Perform ultrasound or abdominal CT scan with contrast If imaging is positive, continue to omit ponatinib and repeat according to clinical care If imaging is negative, or after resolution by imaging, resume at 45 mg after recovery to ≤ grade 1 Recurrence at 45 mg: Repeat above, except resume at 30 mg after recovery to ≤ grade 1 Recurrence at 30 mg: Repeat above, except resume at 15 mg after recovery to ≤ grade 1 Recurrence at 15 mg: Discontinue ponatinib

→ → Use the NCI Common Terminology Criteria for Adverse Events (CTCAE) version 4.0* unless otherwise specified ← ←			
CTCAE System/Organ/Class (SOC)	ADVERSE EVENT	AGENT	ACTION**
	Pancreatitis ≥ Grade 3	Ponatinib	Omit ponatinib Perform ultrasound or abdominal CT scan with contrast If imaging is positive, continue to omit ponatinib and repeat according to clinical care If imaging is negative, or after resolution by imaging, resume at 30 mg after recovery to ≤ grade 1 Recurrence at 30 mg: Repeat above, except resume at 15 mg after recovery to ≤ grade 1 Recurrence at 15 mg: Discontinue ponatinib
	Pancreatitis ≥ Grade 4	Ponatinib	Discontinue ponatinib
Nervous System Disorders	Stroke any Grade	Ponatinib	Discontinue ponatinib
	Peripheral sensory neuropathy ≥ Grade 2	Ponatinib	Please see section 8.43 below for guidance
Cardiac Disorders	Left ventricular systolic dysfunction ≥ Grade 3	Ponatinib	Omit ponatinib Resume at 45 mg after recovery to ≤ grade 1 Recurrence at 45 mg : Omit ponatinib Resume at 30 mg after recovery to ≤ grade 1 Recurrence at 30 mg: Omit ponatinib Resume at 15 mg after recovery to ≤ grade 1 Recurrence at 15 mg: Discontinue ponatinib
	Left ventricular systolic dysfunction ≥ Grade 4		Discontinue ponatinib
	Myocardial Infarction any Grade		Discontinue ponatinib

→ → Use the NCI Common Terminology Criteria for Adverse Events (CTCAE) version 4.0* unless otherwise specified ← ←

CTCAE System/Organ/Class (SOC)	ADVERSE EVENT	AGENT	ACTION**

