10.0 Adverse Event (AE) Reporting and Monitoring

10.1 Adverse Event Characteristics

CTCAE term (AE description) and grade: The descriptions and grading scales found in the revised NCI Common Terminology Criteria for Adverse Events (CTCAE) version 4.0 will be utilized for AE reporting. All appropriate treatment areas should have access to a copy of the CTCAE version 4.0. A copy of the CTCAE version 4.0 can be downloaded from the CTEP web [site](http://ctep.cancer.gov/protocolDevelopment/electronic_applications/ctc.htm): (http://ctep.cancer.gov/protocolDevelopment/electronic_applications/ctc.htm)

10.11 Adverse event monitoring and reporting is a routine part of every clinical trial. First, identify and grade the severity of the event using the CTCAE version 4.0. Next, determine whether the event is expected or unexpected (see Section 10.2) and if the adverse event is related to the medical treatment or procedure (see Section 10.5). With this information, determine whether the event must be reported as an expedited report (see Section 10.). Expedited reports are to be completed within the timeframes and via the mechanisms specified in Sections 10.4. All AEs reported via expedited mechanisms must also be reported via the routine data reporting mechanisms defined by the protocol (see Sections 10.6 and 18.0).

- 10.12 Each CTCAE term in the current version is a unique representation of a specific event used for medical documentation and scientific analysis and is a single MedDRA Lowest Level Term (LLT). Grade is an essential element of the Guidelines and, in general, relates to **severity** for the purposes of regulatory reporting to NCI.

NOTE: A severe AE, as defined by the above grading scale, is **NOT** the same as serious AE which is defined in the table in Section 10.4.

- 10.13 Medical conditions/diseases present before starting study treatment are only considered adverse events if they worsen after starting study treatment (any procedures specified in the protocol). Adverse events occurring before starting study treatment but after signing the informed consent form are recorded. Abnormal laboratory values or test results constitute adverse events only if they induce clinical signs or symptoms or require therapy, and are recorded.

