10.6 Required Routine Reporting

Adverse events to be graded at each evaluation and pretreatment symptoms/conditions to be evaluated at baseline per the CTCAE v4.0 grading unless otherwise stated in the table below:

System Organ Class (SOC)	Adverse event/Symptoms	Baseline	Each evaluation
General disorders and administrations site conditions	Fatigue	X	X
	Fever (Pyrexia)	X	X
	Edema limbs	X	X
Gastrointestinal Disorders	Nausea	X	X
	Vomiting	X	X
	# of stools	X	
	Diarrhea		X
	Constipation		X
	Abdominal pain	X	X
	Rash maculo-papular	X	X
Investigations	Neutrophil count decreased	X	X
	Platelet count decreased	X	X
	Cough	X	X
	Pneumonitis	X	X

10.61 Submit via appropriate MCCC Case Report Forms (i.e., paper or electronic, as applicable) the following AEs experienced by a patient and not specified in Section 10.6:

10.611 Grade 2 AEs deemed *possibly, probably, or definitely* related to the study treatment or procedure.

10.612 Grade 3 and 4 AEs regardless of attribution to the study treatment or procedure.

10.613 Grade 5 AEs (Deaths)

10.6131 Any death within 30 days of the patient's last study

treatment or procedure regardless of attribution to the study treatment or procedure.

10.6132 Any death more than 30 days after the patient's last study treatment or procedure that is felt to be at least possibly treatment related must also be submitted as a Grade 5 AE, with a CTCAE type and attribution assigned.

10.62 Refer to the instructions in the Forms Packet (or electronic data entry screens, as applicable) regarding the submission of late occurring AEs following completion of the Active Monitoring Phase (i.e., compliance with Test Schedule in Section 4.0).

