16.32 Definitions and Analyses of Secondary Endpoints

- 16.321 Progression-free survival time is defined as the time from registration to the earliest date of documentation of disease progression. If a patient dies without a documentation of disease progression the patient will be considered to have had disease progression at the time of their death. In the case of a patient starting treatment and then never returning for any evaluations, the patient will be censored for progression 1 day post-registration. The distribution of progression-free survival time will be estimated using the method of Kaplan-Meier (1958).
- 16.322 Survival time is defined as the time from registration to death due to any cause. The distribution of survival time will be estimated using the method of Kaplan-Meier (1958).
- 16.323 CA 19-9 response is defined to be a $\geq 50\%$ reduction from baseline. The CA 19-9 response rate will be estimated by the number of CA 19-9 responses divided by the total number of evaluable patients. A confidence interval will be calculated based on the binomial distribution.
- 16.324 Adverse Events: All eligible patients that have initiated treatment will be considered evaluable for assessing adverse event rate(s). The maximum grade for each type of adverse event will be recorded for each patient, and frequency tables will be reviewed to determine patterns. Additionally, the relationship of the adverse event(s) to the study treatment will be taken into consideration.

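### Read literally, 10.13 and 10.61 can leave silent, mainly lower-grade LVEF decline out of the 16.324 adverse event table, and that table does not show how many patients had an on-drug echocardiogram

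*Combined protocol and SAP*

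**What the plan says.** **Schedule.** Footnote 10 of Section 4.0 reads "Echocardiograms to be completed at baseline and then every 2 cycles for the duration of study treatment". The on-drug mark sits in the column headed "Cycle 2 and beyond Day 1 (± 2 days) prior to treatment", and the echocardiogram row has no mark under end of treatment. Section 19.2 lists echocardiograms as research funded.

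**When a test result is an adverse event.** Section 10.13: "Abnormal laboratory values or test results constitute adverse events only if they induce clinical signs or symptoms or require therapy, and are recorded".

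**What is collected.** Section 10.6 sets a fixed list, introduced by "Adverse events to be graded at each evaluation and pretreatment symptoms/conditions to be evaluated at baseline per the CTCAE v4.0 grading". It contains no cardiac or ejection fraction term. Events off that list fall under 10.61. Grade 2 is submitted under 10.611 only as "Grade 2 AEs deemed *possibly, probably, or definitely* related to the study treatment or procedure", Grades 3 and 4 are submitted whatever the attribution, and Grade 5 is submitted under 10.613. Grade 1 is not mentioned.

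**Dose rules.** The lowest left ventricular entry in Table 8.2 is "Left ventricular systolic dysfunction ≥ Grade 3". Section 8.3 separately holds the next cycle until other ponatinib-related adverse events are back to Grade 1 or baseline.

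**Analysis.** Section 16.324 takes every eligible patient who started treatment as the denominator and plans this summary: "The maximum grade for each type of adverse event will be recorded for each patient, and frequency tables will be reviewed to determine patterns". It also takes relationship to treatment into account. Section 16 mentions neither echocardiograms nor LVEF.

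**The concern.** Goal 2.22 is to estimate the adverse event profile of ponatinib. Section 9.6 reports heart failure or left ventricular dysfunction of any grade in 8% of treated patients (N = 35), and fatal or serious cases in 5% (N = 22). The trial pays for echocardiograms, which can show a fall before symptoms appear, but the analysis takes in a fall only if it first becomes an adverse event.

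From the 16.324 table alone, a row showing no left ventricular dysfunction has three possible meanings:

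- echoes were done and no one declined;
- some patients declined without symptoms or treatment, and the falls were not counted;
- a number of patients left before any on-drug echo.

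The table cannot separate these. What is at stake is the interpretation of one secondary safety result, mainly for lower-grade change.

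**Working it through.** **1. Path of a symptom-free, untreated LVEF fall through the rules**

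| Grade of fall | 10.13 read literally | If the investigator still calls it an adverse event |
|---|---|---|
| 1 | Not an adverse event | Not collected under 10.61 |
| 2, unrelated | Not an adverse event | Not collected under 10.61 |
| 2, at least possibly related | Not an adverse event | Submitted (10.611); next cycle delayed (8.3) |
| 3 or 4 | Not an adverse event | Submitted (10.612); Table 8.2 acts |

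Table 8.2 treats left ventricular systolic dysfunction as a graded event that requires action, so Grade 3 or higher would probably come to notice. The realistic gap is the lower grades.

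**2. When the first on-drug echo falls.** A cycle is 28 days, so every 2 cycles gives 2 × 28 = Day 56, about Week 8.

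**3. How many treated patients would have one.** The documents do not give time on drug. I assume exponential time on drug with a median of 60 to 120 days. The share still on drug at day t is 2^(−t/median).

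- Day 56, median 60: 2^(−56/60) = 52.4%; × 30 = 15.7, about 16.
- Day 56, median 120: 2^(−56/120) = 72.4%; × 30 = 21.7, about 22.
- Milder case, 10% leaving before Day 56 (assumed): 0.90 × 30 = 27.

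The 30 is the maximum accrual in 16.22.

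**4. Effect on a zero count.** The one-sided 95% upper limit with no events in n patients is 1 − 0.05^(1/n).

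| n | Upper limit |
|---|---|
| 30 (all treated read as tested) | 9.5% |
| 27 | 10.5% |
| 22 | 12.7% |
| 16 | 17.1% |

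**5. Rough scale of the non-serious group.** Section 9.6 gives no denominator, but the 449 in 9.5 fits: 35/449 = 7.8% and 22/449 = 4.9%, against the stated 8% and 5%. The remaining 13 patients are 13/449 = 2.9%, and 2.9% of 30 is about 0.9 patients. Those 13 need not have been silent, and the documents give no silent rate.

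**6. Precision of a change-from-baseline summary.** The 95% half-width is t(0.975, n−1) × SD/√n, with the SD of change assumed to be 5 to 7 points.

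- n = 22, SD 5: 2.080 × 5/4.690 = 2.2 points.
- n = 16, SD 7: 2.131 × 7/4 = 3.7 points.
- Stage 1 stop at 10 patients gives 5 to 7 tested (10 × 0.524 to 0.724). The half-width runs from 2.447 × 5/2.646 = 4.6 to 2.776 × 7/2.236 = 8.7 points.

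**7. Noise in a cut at 50%.** If that SD of change is all measurement error, the per-reading SD is 5/√2 to 7/√2, or 3.5 to 4.9. With true LVEF 55, the chance of a false reading at or below 50% is 7.9% to 15.6% for one reading. For three readings, 1 − (1 − p)³ gives 21.8% to 39.9%. With true LVEF 60, the three-reading figure is 0.7% to 6.4%.

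**8. Is LVEF the only such test?** No. The EKG is first due on drug at the end of Cycle 3, 3 × 28 = Day 84. The same model gives 37.9% to 61.6%, or about 11 to 18 of 30.

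**The case against.** The strongest reply is that the protocol does not apply 10.13 literally. Section 10.6 grades neutrophil and platelet counts, and Table 8.2 grades ALT/AST and amylase. Left ventricular dysfunction is itself in Table 8.2. Once an investigator calls a fall an adverse event, a related Grade 2 fall is submitted and delays the next cycle. What remains uncollected is Grade 1 and unrelated Grade 2, which is the threshold for every term off the 10.6 list. This stands, and it limits the point to lower grades and to what the rules permit.

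The case report forms are not shown, and the Other Laboratory or Evaluation/Treatment forms in 18.1 might hold echo results. This also stands. Even so, collected values would have no planned summary.

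A cut at 50% is noisy, as step 7 shows. That is a reason to make change at the first scheduled echo the main summary and to treat crossings as secondary.

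Four stronger readings are tempting, but the documents do not support them:

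- *Cardiac toxicity will be under-reported.* The text shows only that the rules allow it.
- *LVEF is the only test with this gap.* The EKG schedule in Section 4.0 contradicts that. LVEF is chosen because left ventricular dysfunction is a known ponatinib toxicity (9.6).
- *The first on-drug echo is at Day 28.* The column heading invites this, but footnote 10 points to about Week 8.
- *Safety oversight fails.* Adverse events are assessed every cycle, 16.41 provides for review at least twice a year by the study team and by the DSMB, and 16.42 concerns Grade 4 or higher.

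**Conclusion.** The point holds as a minor one. Followed literally, 10.13 and 10.61 can keep symptom-free, untreated, mainly lower-grade LVEF decline out of the only planned adverse event summary, and 16.324 gives no count of patients with an on-drug echo. Whether this would happen in practice cannot be settled from the documents.

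The size depends on early loss, which is assumed. The difference in the zero-event upper limit is about 1 point if 27 of 30 are tested (10.5% against 9.5%) and about 8 points if 16 are (17.1% against 9.5%). The milder end may be nearer the truth, because the first scheduled scan is at Week 8 and entry requires a life expectancy of at least 3 months. The primary endpoint and the 16.42 stopping rule are unaffected.

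**What to change.** 1. In 10.13, exempt LVEF from the restriction on test results, or add it to the 10.6 list.
2. Record the date and LVEF value of each echocardiogram, if no existing form does so.
3. Add one descriptive table to 16.32 with:
   - the number of treated patients with and without an on-drug echo;
   - change from baseline at the first scheduled on-drug echo, with a 95% CI, as the main summary;
   - among patients with an on-drug echo, the number with LVEF at or below 50% or below the institutional lower limit (the 3.29h entry limits), with echoes per patient and a note that single-reading crossings include measurement noise.

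The cost is a few data fields, one short table and one sentence in 10.13 or 10.6. No tests, patients or alpha are added. The downside is a cardiac figure that will be imprecise, especially after a Stage 1 stop, and may look less favourable.

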6.0 Registration/Randomization Procedures

6.1 To register a patient, access the Mayo Clinic Cancer Center (MCCC) web page and enter the registration/randomization application. The registration/randomization application is available 24 hours a day, 7 days a week. Back up and/or system support contact information is available on the Web site. If unable to access the Web site, call the MCCC Registration Office at (██████████) between the hours of 8 a.m. and 4:30 p.m. Central Time (Monday through Friday).

The instructions for the registration/randomization application are available on the MCCC web page (██████████) and detail the process for completing and confirming patient registration. Prior to initiation of protocol treatment, this process must be completed in its entirety and a MCCC subject ID number must be available as noted in the instructions. It is the responsibility of the individual registering the patient to confirm the process has been successfully completed prior to release of the study agent. Patient registration via the registration/randomization application can be confirmed in any of the following ways:

- Contact the MCCC Registration Office (██████████). If the patient was fully registered, the MCCC Registration Office staff can access the information from the centralized database and confirm the registration.
- Refer to “Instructions for Remote Registration” in section “Finding/Displaying Information about A Registered Subject.”

6.2 Documentation of IRB approval must be on file in the Registration Office before an investigator may register any patients.

In addition to submitting initial IRB approval documents, ongoing IRB approval documentation must be on file (no less than annually) at the Registration Office (fax: ██████████). If the necessary documentation is not submitted in advance of attempting patient registration, the registration will not be accepted and the patient may not be enrolled in the protocol until the situation is resolved.

When the study has been permanently closed to patient enrollment, submission of annual IRB approvals to the Registration Office is no longer necessary.

6.3 Prior to accepting the registration, registration application will verify the following:

- IRB approval at the registering institution
- Patient eligibility
- Existence of a signed consent form
- Existence of a signed authorization for use and disclosure of protected health information

6.4 An optional correlative research component is part of this study, there will be an option to select if the patient is to be registered onto this component (see Sections 14.0 and 17.0).

- Patient has/has not given permission to have a tissue biopsy at cycle 2, day 1.
 - Patient has/has not given permission to allow any excess tissue collected while on this study to be used for research studies
 - Patient has/has not given permission for blood collection at screening, Prior to each cycle, and at end of study to be used for research studies.
- 6.5 At the time of registration, the following will be recorded:
- Patient has/has not given permission for his/her tissue and blood sample(s) to be stored and used in future research of biliary cancer at Mayo Clinic
 - Patient has/has not given permission for his/her tissue and blood sample(s) to be stored and used in future research at Mayo Clinic to learn about, prevent, or treat any other health problems
 - Patient has/has not given permission for Mayo Clinic to give his/her tissue and blood sample(s) to researchers at other institutions
- 6.6 Treatment cannot begin prior to registration and must begin ≤ 7 days after registration.
- 6.7 Pretreatment tests/procedures (see Section 4.0) must be completed within the guidelines specified on the test schedule.
- 6.8 All required baseline symptoms (see Section 10.6) must be documented and graded.
- 6.9a Treatment on this protocol must commence at a Mayo Clinic institution under the supervision of a medical oncologist.
- 6.9b Study drug is available on site.
- 6.9c Patient questionnaire booklet is available on site; copies are not acceptable for this submission.

7.0 Protocol Treatment

7.1 Treatment Schedule

Agent	Dose Level	Route	Day
Ponatinib	45mg once daily	PO	Days 1-28

- 7.2 For this protocol, the patient must return to the consenting institution for evaluation at least every 28 days (+/- 2 days) during treatment (Active Monitoring Phase).
- 7.3 Patients should receive low-dose aspirin (e.g. 81mg/day), as prophylaxis against arterial thrombotic events, if not contraindicated.
- 7.4 Patients should receive treatment with a statin, as prophylaxis against arterial thrombotic events, if not contraindicated. Atorvastation, 10-20 mg per day, is suggested.

